Project code	EpidProtect-21
Study title	Exhaustive, cross-sectional, non-interventional, multicenter retrospective epidemiological study of the COVID-2019 incidence and prevention methods of SARS, including COVID-2019, among staff of participating organizations.
Version of Synopsis	0.2, 15.02.2021.
Justification of study	
Coronaviruses are a large family of viruses that might cause illness in animals or humans. SARS-CoV-2 is an enveloped, single-stranded RNA virus of the β genus. It can cause respiratory illness named COVID-19, the severity of which varies from asymptomatic to severe, and which can lead to the patient's death or long-term consequences (so-called post-COVID syndrome). The virus has spread globally and been declared a Public Health Emergency of International Concern by WHO in January 30, 2020.
 
The first case of COVID-19 in Ukraine was detected in early March, 2020. 1273475 cases of the disease have been registered in Ukraine as at February 15, 2021.
 
Quarantine restrictions and other anti-epidemic measures established in Ukraine and their results are the subject of wide debate.
 
Own anti-epidemic measures, in addition to those established by the Government, have also been implemented by numerous representatives of the public sector, non-governmental organizations and business.
 
The company management of the participating organizations decided to provide their staff with prophylactic tools and recommendations for COVID-19 prevention.
 
The study aims to identify the incidence, characteristics of cases and their relationship with the preventive measures used.

Study design	Exhaustive, cross-sectional, non-interventional, multicenter retrospective epidemiological study, case study.
Number of subjects	3443 subjects.

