Location of study conduct	
Each subject will participate in the study in the participating organization by which the subject is employed:
 
• SI National Institute of Phthisiology and Pulmonology named after F.G. Yanovsky.• Yuria-Pharm LLC.• Infuzia PJSC.• Institute Hyalual LLC.• Medical Center M.T.K. LLC.• InterChem SLC.• Diatom LLC. 
For the study the following facilities will be organized at each participating organization:
 
• Specially designated locations for material collection and conduction of rapid ELISA tests for the antibodies to COVID-2019.• Specially designated computerized places for questionnaires with assigned staff who organize the order and accuracy of the questionnaire conduct.
Duration of data collection	3 months.
Purpose of the study	To determine the relationship between the systematic use of prophylactics to prevent SARS, including COVID-2019, and the risks of incidence and serious complications of COVID-2019 among staff of participating organizations.
Study objectives	
• To investigate the incidence of COVID-2019 cases in participating organizations.• To investigate the severity of the COVID-2019 cases in participating organizations.• To explore the prevention methods used by staff members.• To determine the relationship between the used prevention methods and incidence of COVID-2019 among staff of participating organizations.

	
• To determine the relationship between the presence of comorbidities, such as bronchial asthma and COPD, and the incidence/severity of COVID-2019.• To determine the relationship between the COVID-2019 case and the course of comorbidities, such as bronchial asthma and chronic obstructive pulmonary disease (COPD).• To identify the relationship between different strategies and combinations of drugs used for prophylactics at any time from March 2020 and the risk of having a COVID-2019 case.• To identify the relationship between different strategies and combinations of drugs used for prophylactics at any time from March 2020 and the risk of having a severe COVID-2019 case.• To identify the relationship between different strategies and combinations of drugs used for prophylactics at any time from March 2020 and the risk of hospitalization of persons who had at least one COVID-2019 case.

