Study endpoints	
• The incidence of COVID-2019 cases in participating organizations.• The severity of the COVID-2019 cases in participating organizations.• Prevention methods of SARS, including COVID-2019, which were used by subject who had at least one COVID-2019 case.

	
Prevention methods of SARS, including COVID-2019, which were used by subject who did not have any COVID-2019 case.Relationship between the used prevention methods and incidence of COVID-2019 among staff of participating organizations.Relationship between the presence of comorbidities, such as bronchial asthma and COPD, and the incidence/severity of COVID-2019 case.Relationship between the COVID-2019 case and the course of comorbidities, such as bronchial asthma and chronic obstructive pulmonary disease (COPD).Relationship between different strategies and combinations of drugs used for prophylactics at any time from March 2020 and the risk of having a COVID-2019 case.Relationship between different strategies and combinations of drugs used for prophylactics at any time from March 2020 and the risk of having a severe COVID-2019 case.Relationship between different strategies and combinations of drugs used for prophylactics at any time from March 2020 and the risk of hospitalization of subjects who had at least one COVID-2019 case.
Study variables	
Demographic characteristics: age, gender.Anthropometric characteristics: body weight, height.Blood group.Number of people in the household.Lifestyle: the presence of bad habits, physical activity, diet.Medical history: comorbidities, their treatment.Prevention methods of SARS, including COVID-2019, currently used by the subject.Number of COVID-2019 cases, which subject had.Characteristics of the disease case, its treatment.

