	
Prevention methods of SARS, including COVID-2019, which were used by subject who had at least one COVID-2019 case.Prevention methods of SARS, including COVID-2019, which were used by subject who did not have any COVID-2019 case.Amount of costs spent on prevention and treatment of SARS, including COVID-2019.Relationship between different strategies and combinations of drugs used for prophylactics at any time from March 2020 and the risk of having a COVID-2019 case.Relationship between different strategies and combinations of drugs used for prophylactics at any time from March 2020 and the risk of having a severe COVID-2019 case.Relationship between different strategies and combinations of drugs used for prophylactics at any time from March 2020 and the risk of hospitalization of subjects who had at least one COVID-2019 case.
Inclusion criteria	Subjects who meet all the inclusion criteria will be included in the study: 
The subject gave the consent to participate in the study and signed the consent to processing of personal data.The subject aged 18 years and older.The subject is employed by one of the participating organizations.
Exclusion/withdrawal criteria	The nature of the study does not provide for withdrawal criteria. The subject may not be included in the study due to non-compliance with the inclusion criteria or due to force majeure.
Calculation of sample size	Not applicable as it is exhaustive study. Participating organizations undertake to organize the involvement in the study of at least 95% of persons employed by participating organizations.

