The relationship between the subject's characteristics and the variables of interest will be assessed using a one-dimensional and multidimensional (polynomial) logistic regression model for variables, which have no more than 20% omitted data.

The final model will be selected with a view to minimizing the Akaike information criterion value.

2×2 tables, χ^2 -square were used for calculations of odds ratios.

Rough odds ratios and adjusted odds ratios with corresponding 95% confidence intervals and p-values will be generated and presented for both one-dimensional and multidimensional logistics models.

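### The plan names only χ² 2×2 tables and logistic regression, with no provision for sparse or zero cells when drug combinations are related to severe cases and hospitalization

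*Combined protocol and SAP*

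**What the plan says.** Under Statistical analysis plan, the combined document says that 2×2 tables with χ² "were used for calculations of odds ratios". Relationships are to be assessed with a "one-dimensional and multidimensional (polynomial) logistic regression model for variables, which have no more than 20% omitted data". The final model is the one with the lowest AIC. Crude and adjusted odds ratios, each with a 95% confidence interval and a p-value, are to be presented from the logistic models.

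Under Study objectives, Study endpoints and Study variables, these tools have to serve three questions about "different strategies and combinations of drugs used for prophylactics": the risk of any case, the risk of a severe case, and "the risk of hospitalization of subjects who had at least one COVID-2019 case".

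Number of subjects gives "3443 subjects". Calculation of sample size says "Not applicable as it is exhaustive study", so no event count was projected. No section gives an attack rate, a severe-case or hospitalization rate, the frequency of any prophylactic, or the number of combinations to be compared. No section mentions exact tests, penalised likelihood, a continuity correction, a minimum cell or event count, or merging of rare combinations.

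**The concern.** The number 3443 counts people, not events. Hospitalization is studied only among those who had a case, and that smaller set is then divided by drug combination. An uncommon combination may have very few hospitalized users, or none.

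With none, the sample odds ratio is exactly 0. The usual standard error of its logarithm contains a division by zero, and the ordinary logistic likelihood has no finite maximum for that term (separation). The χ² approximation is also poor when an expected count is well below 5.

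At stake are the results on the most serious outcomes. A combination with a few dozen users and no hospitalization could be tabulated with an odds ratio of 0 although chance alone readily produces that result, and the interval beside it would carry no information.

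**Working it through.** There is no figure of the plan's own to reproduce: 3443 is a census count. The check therefore asks how often zero cells could arise, and what the named methods do when one occurs.

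**Inputs.** From the documents: N = 3443. Assumed, because the documents give no values:
- proportion with a case: 10% to 30%;
- proportion of cases hospitalized: 3% to 15%;
- share of cases using a given combination: 1% to 5%.

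**Formulas.** Cases = 3443 × proportion with a case. Users = cases × share. Expected events = users × proportion hospitalized. Chance of no event, if the combination has no effect = (1 − proportion hospitalized)^users.

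**Results** (users rounded to whole persons):

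| With a case / hospitalized | Cases / events | Share | Users | Expected events | Chance of none |
|---|---|---|---|---|---|
| 10% / 3% | 344 / 10 | 5% | 17 | 0.51 | 0.97^17 = 0.60 |
| 20% / 5% | 689 / 34 | 5% | 34 | 1.7 | 0.95^34 = 0.175 |
| 20% / 5% | 689 / 34 | 2% | 14 | 0.70 | 0.95^14 = 0.49 |
| 30% / 15% | 1033 / 155 | 5% | 52 | 7.8 | 0.85^52 = 0.0002 |
| 30% / 15% | 1033 / 155 | 1% | 10 | 1.5 | 0.85^10 = 0.20 |

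The number of combinations matters as much as the rates. With 16 equal-sized combinations, the chance of at least one zero cell is 0.998 (10% / 5%), 0.85 (20% / 5%), 0.16 (20% / 10%) and 0.02 (30% / 10%). With four, it is at most 0.05 in all four settings.

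For the any-case outcome, a combination used by 5% of staff expects 17 cases (3443 × 0.05 × 0.10) to 52 cases (3443 × 0.05 × 0.30). Sparsity is therefore mainly a matter for the two rarer outcomes.

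**What the named methods give.** Take the 20% / 5% setting with 34 users and no event: 0/34 against 34/655.
- Sample odds ratio: (0 × 621)/(34 × 34) = 0.
- Ordinary logistic regression: no convergence; log odds ratio about −22.8, standard error about 64,000, Wald p about 1.00.
- Smallest expected cell: 34 × 34/689 = 1.68. Pearson χ² p = 0.17; Fisher exact p = 0.40.
- With 0.5 added to each cell: odds ratio (0.5 × 621.5)/(34.5 × 34.5) = 0.26, 95% interval 0.016 to 4.35. This is finite and plainly uninformative, as it should be.

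**What AIC does.** One added term is kept if its likelihood-ratio gain exceeds 2. For a zero-event combination against all other cases:
- 689 cases, 34 events, 34 users: gain 3.53, kept.
- 689 cases, 34 events, 20 users: gain 2.05, kept (19 users: 1.95, dropped). The chance of no event at 20 users is 0.95^20 = 0.36.
- 689 cases, 34 events, 14 users: gain 1.43, dropped.
- 344 cases, 10 events, 17 users: gain 1.03, dropped.

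In the 20% / 5% setting, AIC therefore carries the inestimable term forward from about 20 users upward and removes it in smaller groups.

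**The case against.** The strongest reply is that this is a synopsis-level text that defers all main steps to a separate Statistical Analysis Plan. The 2×2 sentence names no outcome, and maximum likelihood is not named as the fitting method. A reader might infer that the plan commits every outcome to methods that must fail. The documents do not support that: exact or penalised methods are unmentioned, not excluded. This part of the reply stands.

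A reader might also infer that sparse cells are certain, or that most combinations would be affected. That is not supported either. No rates or number of combinations are given, and under high event rates or with few combinations the problem nearly disappears. Nor does AIC always favour a separated term, as the smaller examples above show.

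The reply adds that the analysis is described as mainly descriptive, without pre-defined hypotheses, and that a standard error of about 64,000 beside an odds ratio of 0 is visibly uninformative. In the worked table neither p-value is significant. This softens the harm but does not remove it: odds ratios, intervals and p-values are still promised, and an interval that cannot be used is no description.

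Finally, separate analyses in subpopulations are conditional on there being enough data. That guard is undefined and concerns subpopulations, not the cells of an exposure table or the terms of a model.

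**Conclusion.** The point holds as a minor one. The only inferential methods named are χ² 2×2 tables and logistic regression with AIC selection, and nothing provides for sparse or zero cells in the analyses of severe cases and hospitalization by drug combination. Where a zero cell occurs, those methods in their ordinary form give an odds ratio of 0, no usable interval and an unreliable χ² p-value.

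How often this happens cannot be known from the documents. Under the assumed ranges, the chance of no hospitalized user for a combination used by 5% of cases runs from 60% (10% / 3%) through about 17% (20% / 5%) to practically nil (30% / 15%).

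These figures are for hospitalization. They carry over to severe cases only if the severe-case rate is similar and the analysis is confined to cases; the endpoint "combinations of drugs used for prophylactics at any time from March 2020 and the risk of having a severe COVID-2019 case" is not expressly so confined. The any-case outcome is largely unaffected.

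**What to change.** In the separate Statistical Analysis Plan, before the data are analysed:

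1. For the severe-case and hospitalization models, fit Firth-penalised logistic regression and report profile-likelihood 95% confidence intervals.
2. For any 2×2 table with an expected cell below 5, use an exact test and interval (Fisher or mid-P) in place of χ².
3. Optionally, pre-specify a rule for merging rare combinations before modelling. The cut-off is the sponsor's choice.

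The cost is a few lines of text and standard software options. The price in the results is slight shrinkage of the estimates and somewhat conservative exact p-values. If the merging rule is adopted, rare combinations are also no longer reported separately.

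### One AIC selection rule, with no adjustment set for each exposure, serves both the prophylaxis and the asthma/COPD objectives, so the meaning of the adjusted asthma/COPD odds ratio is left to predictive fit

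*Combined protocol and SAP*

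**What the plan says.** Study objectives sets two kinds of exposure question. One is "To determine the relationship between the used prevention methods and incidence of COVID-2019 among staff of participating organizations", extended in later objectives to drug strategies and the risks of a case, a severe case and hospitalization. The other is "To determine the relationship between the presence of comorbidities, such as bronchial asthma and COPD, and the incidence/severity of COVID-2019". Study endpoints repeats both.

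The Statistical analysis plan section gives one method for all of them: "The relationship between the subject's characteristics and the variables of interest will be assessed using a one-dimensional and multidimensional (polynomial) logistic regression model". The only entry rule is that it is used "for variables, which have no more than 20% omitted data". Then: "The final model will be selected with a view to minimizing the Akaike information criterion value". The reporting rule is "Rough odds ratios and adjusted odds ratios with corresponding 95% confidence intervals and p-values will be generated and presented", and this is to be done "for both one-dimensional and multidimensional logistics models".

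No covariates are named for any exposure, and no term is forced in or kept out. Study variables lists comorbidities and prevention methods alike, so both are candidates for any model. The section also calls the analysis mainly descriptive and refers to a separate analysis plan for the detailed steps.

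**The concern.** The two questions need different covariates. For prophylaxis, asthma/COPD is a plausible confounder: it may affect both who takes prophylaxis and who falls ill, so it belongs in the model. For asthma/COPD, prophylaxis may come after the exposure, because staff with lung disease may protect themselves more. Adjusting for it then removes the part of the association that runs through protective behaviour.

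AIC rewards predictive fit and does not distinguish a confounder from an intermediate variable. Under the stated rule, the data decide whether the reported asthma/COPD odds ratio is an overall association or an association at fixed prophylaxis use, and whether asthma/COPD stays in the model at all. A reader of the results table would probably take the figure as the risk that goes with the disease, without knowing which quantity it is.

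**Working it through.** The plan has no figure to reproduce. The 3443 subjects are a headcount, and the sample size calculation is declared not applicable. All other inputs below are assumptions for illustration.

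**1. Overall odds ratio against odds ratio at fixed prophylaxis.** Assume a logistic model without interaction. Let o be the odds of COVID-19 in non-users without asthma/COPD, A the asthma/COPD odds ratio at fixed prophylaxis, and P the prophylaxis odds ratio. The odds are o (non-user, no disease), oP (user, no disease), oA (non-user, disease) and oAP (user, disease). Each converts to a risk as odds/(1 + odds). The risk in each disease group is the average over its users and non-users. The overall odds ratio compares the two averaged risks.

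Worked example: baseline risk 25% (o = 1/3), A = 1.5, P = 0.5, prophylaxis use 40% without and 70% with asthma/COPD.

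- Without disease: 0.6 × 0.2500 + 0.4 × 0.1429 = 0.2071
- With disease: 0.3 × 0.3333 + 0.7 × 0.2000 = 0.2400
- Overall odds ratio: (0.2400/0.7600) / (0.2071/0.7929) = 1.21, against 1.5 at fixed prophylaxis

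With equal use of 40% in both groups and the other inputs unchanged, the overall odds ratio is 1.49. Non-collapsibility of the odds ratio therefore explains only about 0.01 of the gap. The rest is the path through prophylaxis.

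The same formula with baseline risk 20%, A = 1.5 and 40% use without asthma/COPD gives these overall odds ratios:

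| Prophylaxis odds ratio | Use with asthma/COPD 40% | 50% | 60% | 80% |
|---|---|---|---|---|
| 1.0 | 1.50 | 1.50 | 1.50 | 1.50 |
| 0.8 | 1.50 | 1.47 | 1.43 | 1.37 |
| 0.6 | 1.49 | 1.42 | 1.35 | 1.21 |
| 0.4 | 1.48 | 1.36 | 1.24 | 1.02 |

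There is no gap if prophylaxis has no effect, and almost none if use is equal. The gap grows with both the effect and the difference in use.

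**2. What AIC would keep.** A simulation used 3443 subjects, 300 replicates per scenario, baseline risk 20%, assumed asthma/COPD prevalence 5%, and prophylaxis use 60% with and 40% without asthma/COPD. In each replicate, minimum AIC chose among four models: neither term, either one alone, or both. With a true asthma/COPD odds ratio of 1.5:

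| True prophylaxis odds ratio | Prophylaxis kept | Asthma/COPD kept | Both kept |
|---|---|---|---|
| 1.0 | 15% | 81% | 12% |
| 0.8 | 87% | 77% | 67% |
| 0.6 | 100% | 76% | 76% |

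Prophylaxis is usually dropped only when it has no effect, and then adjusting for it hardly matters. When it does have an effect it is usually kept, and that is when the two odds ratios differ. Asthma/COPD, although truly associated here, is dropped in 19% to 24% of samples (100% minus 81% and 76%), leaving its objective without an adjusted estimate.

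**The case against.** Three stronger readings are tempting, and the documents support none of them.

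- *A single model supplies both adjusted odds ratios.* A reader might infer this from "The final model will be selected", but the next lines speak of models in the plural, and cases, severe cases and hospitalization cannot share one model. The sentence can mean one selected model per analysis.
- *The asthma/COPD odds ratio is adjusted for prophylaxis.* That depends on the missingness limit and on AIC. The plan does not state it.
- *The plan therefore fails its asthma/COPD objective.* The objective asks for a relationship and does not define it as a total effect. Crude odds ratios, free of prophylaxis adjustment, are also planned.

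It is also fair to say that nothing in the documents states that lung disease leads to more prophylaxis. Justification of study says that management supplied staff with prophylactic tools, a cause of use that need not depend on lung disease. Study limitations already warns that direction cannot always be determined. The analysis is mainly descriptive, and the separate analysis plan may hold more detail.

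These points limit the claim but do not remove it. Separate models per outcome still leave both exposures under one selection rule within each outcome. The crude odds ratio is not adjusted for age or smoking, so nothing planned guarantees an asthma/COPD estimate that is adjusted for confounders and free of prophylaxis. A general caveat about direction does not define what is estimated. And whatever is deferred, the text already commits to AIC selection and to adjusted odds ratios with p-values.

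**Conclusion.** The point holds as a conditional one and should be changed before analysis. The plan commits to a selection rule that leaves undefined what the adjusted asthma/COPD odds ratio estimates. It is not a demonstrated error in a result.

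The size depends on two things the documents do not give: how strongly prophylaxis is associated with COVID-19, and how much its use differs by asthma/COPD status. Against an assumed 1.5 at fixed prophylaxis, the overall odds ratio is 1.50 when prophylaxis has no effect, 1.48 to 1.50 when use is equal, about 1.2 to 1.4 over most of the unequal-use range, and 1.02 at the extreme. If asthma/COPD does not influence prophylaxis use, what remains is the lack of exposure-specific covariates and the risk that AIC drops the exposure of interest.

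**What to change.** Replace the AIC rule for adjusted estimates with exposure-specific models, fixed before the data are analysed. For each outcome:

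- **Prophylaxis models:** keep the prophylaxis term whatever its AIC. Adjust for age, sex, BMI, smoking, household size, participating organization and comorbidity including asthma/COPD.
- **Asthma/COPD models:** keep the asthma/COPD term whatever its AIC. Adjust for pre-specified confounders, for example age, sex, smoking, BMI, household size and organization, and leave prophylaxis out. Report the version with prophylaxis added as a labelled sensitivity analysis, described as the association at fixed prophylaxis use.
- **Reporting:** interpret only the odds ratio of the exposure each model was built for. AIC may stay for a separate, labelled exploratory model.

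The covariates are already collected or follow from what is collected: BMI from weight and height, organization from the place of employment. Smoking is not named and is assumed to be recorded under lifestyle. The cost is a change of wording, a few extra models and longer tables, with no new data.

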Study limitations	
Persons, who were employed by one of the participating organizations from March 1, 2020, but who do not have employment relations with the participating organizations during the study period or persons who are on maternity leave, will not be included in the study.
 
Another study limitation is duration of data collection (due to long-term data collection there is a difference in the duration of action of the exposure factor).
 
The retrospective study design has limitations on the completeness and accuracy of the data provided by the study subjects.
 
There may be difficulties in filling in the missing data.
 
Certain relationships can be difficult to describe.
 
The direction of the relationship cannot be determined for all relationships (there may be an inverse relationship).
 
Potential data distortion may be due to the subject selection; use of an electronic data collection system; possible low computer literacy of some subjects; lack of data verification and query generation.
 
The completeness and correctness of the description of available medical documentation for fatal cases of COVID-2019 depends on the amount of information provided and its quality. Conclusions from it cannot be extended to other population members.

-------------------	---

Statistical analysis plan

In the context of this data analysis, all the main steps from the primary data to the results of the study will be described separately in the Statistical Analysis Plan.

This study is not intended to accept or reject pre-defined hypotheses, thus statistical analysis will mainly be descriptive.

All types of analysis will be done for the entire available study population with available data.

If there is a sufficient amount of data in the subpopulations, a separate statistical analysis will be performed.

No conditional calculation methods will be applied to the missed values.

The statistical generalization will consist of frequency tables of categorical variables (number, %).

For metric variables, descriptive statistics (number of subjects with available observations, number of missed values, mean, standard deviation, median, 25th and 75th percentiles, minimum and maximum) will be presented in tabular form.

Statistical conclusions will be used to assess the potential relationship between the identified variables and the incidence / severity of COVID-2019.

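### The purpose and three endpoints ask about risk, but the analysis text plans only odds ratios; adjusted risks, risk differences and risk ratios should be added, which matters most if an outcome is common

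*Combined protocol and SAP*

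**What the plan says.** The Purpose of the study is to relate systematic use of prophylactics to "the risks of incidence and serious complications of COVID-2019 among staff of participating organizations". Under Study objectives and Study endpoints, three items relate prophylaxis strategies and drug combinations to a risk. The first is "the risk of having a COVID-2019 case". The others are the risk of a severe case, and the risk of hospitalization among people who had at least one case.

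The design is described as exhaustive, with "3443 subjects". Calculation of sample size reads "Not applicable as it is exhaustive study" and adds an undertaking to secure "involvement in the study of at least 95% of persons employed by participating organizations". The inclusion criteria are consent, age 18 or over and current employment, so having had the disease plays no part in selection.

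The Statistical analysis plan section names univariable and multivariable logistic regression, with the final model chosen by AIC. The 2×2 tables are used to calculate odds ratios. The reported output is: "Rough odds ratios and adjusted odds ratios with corresponding 95% confidence intervals and p-values will be generated and presented". Frequency tables with number and percentage are also planned. The supplied text specifies no risk ratio, risk difference or standardised risk.

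**The concern.** The question is put on the risk scale and the answer on the odds scale. The usual reason for having to rely on odds ratios is sampling by outcome, and that does not apply here.

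Three things are at stake:

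- A reader who takes an odds ratio for a prophylactic strategy as the proportionate change in risk, as the objectives invite, will see too large an effect when the outcome is common.
- No adjusted absolute difference is planned, so nobody can say how many cases per 100 staff separate two strategies. This is missing whatever the outcome frequency.
- Crude and adjusted odds ratios will be shown together. Because the odds ratio is non-collapsible, the two can differ without confounding, and the difference could be misread as confounding removed.

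**Working it through.** **Inputs.** The plan gives no sample-size calculation, expected incidence, severity rate, hospitalization rate or effect size, so it has no figure to reproduce. Its one case count, 1273475 registered cases nationally, comes without a denominator and gives no rate. The risk in the comparison group, p0, is therefore an assumption, varied here from 5% to 40%.

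**Step 1: odds ratio implied by a given risk ratio.** With p1 = RR × p0,

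OR = [p1/(1 − p1)] / [p0/(1 − p0)].

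Example: p0 = 0.20 and RR = 0.70 give p1 = 0.14, and OR = (0.14/0.86)/(0.20/0.80) = 0.163/0.25 = 0.651.

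| Assumed p0 | OR when RR = 0.70 | Reduction if the OR is read as an RR (true 30%) | Risk difference, points | OR when RR = 0.50 |
|---|---|---|---|---|
| 5% | 0.689 | 31.1% | −1.5 | 0.487 |
| 10% | 0.677 | 32.3% | −3.0 | 0.474 |
| 20% | 0.651 | 34.9% | −6.0 | 0.444 |
| 30% | 0.620 | 38.0% | −9.0 | 0.412 |
| 40% | 0.583 | 41.7% | −12.0 | 0.375 |

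The gap is negligible at 5%, small at 10% and material from about 20%. The same RR of 0.70 goes with a risk difference anywhere from 1.5 to 12 points, which the odds ratio alone does not reveal.

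**Step 2: the two measures with their intervals.** Assume all 3443 subjects are in the denominator, half exposed, with p0 = 30% and RR = 0.70. The odds ratio is 0.620 (95% CI 0.531 to 0.724) and the risk ratio 0.70 (0.623 to 0.787). For hospitalization the denominator is people with a case, so the intervals would be wider.

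**Step 3: non-collapsibility without confounding.** Take two equal strata, balanced on exposure, with unexposed risks of 10% and 40% and a within-stratum odds ratio of 0.50.

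- Covariate odds ratio: (0.40/0.60)/(0.10/0.90) = 6, a strong predictor.
- Exposed odds: 0.111 × 0.5 = 0.0556 and 0.667 × 0.5 = 0.333, so the exposed risks are 5.26% and 25%.
- Average risks: unexposed (10% + 40%)/2 = 25%; exposed (5.26% + 25%)/2 = 15.1%.
- Crude OR: (0.151/0.849)/(0.25/0.75) = 0.535, against an adjusted 0.50.

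With a balanced binary covariate of odds ratio 3, the crude value is only 0.503 at p0 = 5%, 0.512 at 20% and 0.522 at 40%. With several predictors together (normal linear predictor, SD 1.0) it is 0.516 at 5%, 0.543 at 20% and 0.553 at 30%. In that last setting an adjusted odds ratio of 0.50 corresponds to a marginal risk ratio of 0.64 and a risk difference of −10.8 points. If the exposure has no effect, or the covariates do not predict the outcome, there is no such shift.

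**Step 4: whose risk can be estimated.** Enrolment does not depend on outcome, so risks are estimable, but only for part of the workforce since March 2020. Under Study limitations, former employees are left out, and "persons who are on maternity leave, will not be included in the study". Under Methodology, subjects enter their own data and fatal cases are described separately from medical documentation. The population is therefore current, surviving employees who take part.

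**The case against.** The strongest case against the point runs as follows.

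- **Nothing shows that any outcome is common.** This stands, so the overstatement is conditional. The three endpoints may also have different frequencies. A reader might infer that the planned odds ratios will exaggerate the effect; the documents do not support that without an outcome frequency.
- **The odds ratio is a valid, standard measure and the plan labels it correctly.** This also stands. A reader might infer that the planned analysis is wrong. It is not: the overstatement arises only when an odds ratio is read as a risk ratio.
- **The crude-adjusted gap is small and the plan nowhere interprets it as confounding.** Largely right. The 0.535 example needs a covariate odds ratio of 6, so this part is secondary.
- **The denominators are incomplete.** A reader might infer from the word exhaustive that risks for the full workforce are available. They are not, for the reasons in Step 4. The 95% figure is an undertaking and not an achieved rate, and Study limitations concedes that exposure duration differs because collection is prolonged. This narrows the population to which the risks apply but does not stop them being estimated.
- **Absolute risks are already covered.** In part. Incidence and severity are endpoints, and percentages will be tabulated. These are raw percentages, with no specified risk contrast, interval or adjustment.
- **A separate statistical analysis plan is mentioned and may add risk measures.** Possible. The statement that only odds ratios are planned is confirmed for the supplied text alone.
- **Standardised risks by strategy could read as causal.** A fair warning, since Study limitations says the direction of a relationship cannot always be determined. It is a reason to report them alongside the odds ratios with careful wording, not to omit them.

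**Conclusion.** The point holds as a mismatch between the question asked and the measures reported, with a conditional size. If a baseline risk is about 20% or more, an odds ratio read as a change in risk overstates it noticeably: a true 30% reduction reads as 35% at 20% and 38% at 30%. At 5% it reads as 31%, which does not matter. These figures rest on assumed baseline risks. Non-collapsibility is a minor addition that needs a non-null effect and predictive covariates.

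The absence of an adjusted absolute comparison does not depend on outcome frequency, and the planned frequency tables do not fill it. The matter is one of interpretation. It does not invalidate the logistic analysis, and a risk scale would not cure selection, recall or reverse-direction problems. The change is worth making because it answers the stated question more directly at little cost.

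**What to change.** In the regression paragraph of the Statistical analysis plan section, keep the logistic models and the crude and adjusted odds ratios, and add the following:

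1. For each of the three risk endpoints, report the marginally standardised risk under each prophylaxis strategy from the adjusted logistic model, with the risk difference, risk ratio and 95% CI.
2. Keep the prophylaxis term in the model whatever AIC selection does with the other variables; otherwise the contrast may vanish from the final model.
3. State the denominator for each endpoint. If severity is modelled in several categories, state which of them count as severe before standardising.
4. Describe these results as adjusted associations among current participating employees, not as causal effects.
5. Note that a difference between crude and adjusted odds ratios is not by itself evidence of confounding.

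The cost is a few lines of text and some code, with no new data. The downside is a little more analysis work, and effects that look slightly less favourable than the odds ratios.
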